9.4.3 Data Collection Schedule

Cognitive assessments will be performed at v00 (baseline) and at study visits v18 and v36.

9.4.4 Responsibilities of Cognitive Tester

- 1) Follow protocol for cognitive testing and obtain cognition data on each participant at scheduled study visits.
- 2) Follow protocol for analysis and summarization of cognitive data and obtain study measures.

- 3) Enter cognitive summary data into trial data system as it is completed.
- 4) Work with the DCC personnel in rectifying data errors.

9.4.5 DCC Responsibilities

- 1) Monitor timeliness of data entry by study cognitive tester.
- 2) Review newly entered cognition data for completeness. This will include identification of any missing cognition data as well as identification of missing/inaccurate data within a cognitive assessment.
- 3) Review new cognitive data for accuracy. This will include identification of errors in study visit numbers, dates and possible outliers in cognitive data.
- 4) Work with study cognitive tester in rectifying missing/inaccurate data.
- 5) Once new cognition data are deemed clean, update master cognition database.

9.5 DCC Tasks

9.5.1 Data Entry

Prior to data entry, all forms will be inventoried and undergo a 2-step review (study coordinator and data monitor) for completeness and apparent accuracy; incomplete/inaccurate forms are returned to the study coordinator for rectification. Key features of the data entry system at the time of data entry will include: data entry screens that mimic the data forms, must-enter fields for key variables and range checks. A random sample of study data will be double entered by 2 individuals and program-compared to monitor data entry error rates and to identify need for remediation of data entry processes. Data from external laboratories will be entered directly into the trial data system by personnel at the external laboratories. Hard copies of the laboratory data will also be routinely obtained by the DCC to verify the accuracy of data entry.

9.5.2 Study Reports

9.5.2.1 Recruitment and Study Progress

For each meeting of study personnel as well as the External Data Safety Monitoring Board (EDSMB), a report of recruitment and participant progress throughout the study will be generated. The recruitment portion of the report will include numbers of participants prescreened by telephone and reasons for ineligibility, numbers of participants screened in the ARU research clinic and reasons for ineligibility and numbers of participants randomized. The study progress portion of the report will include numbers of participants who have completed various phases of the study up to the date of the report, numbers of study dropouts and reasons for dropouts.

9.5.2.2 Ideal Clinic Visit Schedule

As each participant is randomized, a schedule of "ideal" visit dates and visit windows will be generated by the trial data system. An ideal visit date is defined to be the exact date on which the clinic appointment should occur, given the participant's randomization date and the study visit schedule. The

visit windows will be computed as the ideal visit date, plus or minus fourteen (14) days.

Each participant's ideal visit schedule will be generated at randomization. The ideal schedule will be available to clinic personnel through the trial data system, with an option to print the schedule as needed. The ideal visit schedule will be used to monitor missed visits and compliance to visit schedule (in/out of window visits).

9.5.2.3 Data Quality

The data quality report will be generated on a monthly basis and for the EDSMB, and will include data on the numbers of errors in completion of study forms. Inaccuracies as well as incompleteness in data forms will be considered errors and will be reported separately. Errors will be computed by study form and will be presented since the last report (i.e., in the past month) and on a cumulative basis.

The data quality report will also include reports of data queries, including number of queries responded to, timeliness of response and number of outstanding data queries.

This report will also include summarization of missed visits and visits outside of the ideal visit window.

9.5.2.4 Participant Safety and Adverse Events

For the EDSMB, the DCC will generate a safety report enumerating the following events, both on a cumulative basis (from the start of the study to present) and new events in the past year. For the EDSMB, adverse events will be presented by blinded study group.

- 1) Laboratory chemistry values out of range (enumerating abnormally low and high values separately). This will be separately reported for first time versus repeated abnormalities.
- 2) Triglycerides >500 mg/dL. First time versus repeated elevations will be separately reported.
- 3) Out of range coagulation and hemostatic factors, PT, aPTT, fibrinogen and platelet count (enumerating abnormally low and high values separately). This will be separately reported for first time versus repeated abnormalities.
- 4) Abnormal bleeding events ascertained from the Bleeding Assessment Questionnaire [**FORMS 6a, 6b**].
- 5) Abnormal urine dipstick.
- 6) Major cardiovascular events: fatal/nonfatal MI, sudden coronary death, hospitalization for unstable angina, and revascularization procedures (CABG and PTCA).
- 7) Major cerebrovascular events: TIA, RIND, CVA.
- 8) Peripheral vascular events including surgical reconstruction and bypass.
- 9) Deep vein thrombosis
- 10) Pulmonary thromboembolism

- 11) Cancers
- 12) Deaths
- 13) Other adverse events; serious and non-serious

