1.1 Executive Summary

The potential for nattokinase to “thin” blood and to reduce blood clotting by positive antithrombotic and fibrinolytic effects presents a unique opportunity to safely study such effects on cardiovascular disease (CVD) and cognition. Unfortunately, such studies of antithrombotic and fibrinolytic pathways of prevention have been limited due to lack of safe compounds and the adverse reactions associated with current agents such as Coumadin. Nattokinase, an over-the-counter supplement used for cardiovascular health, is the most active functional constituent of natto, a fermented soy product. Natto has been consumed primarily by the Japanese for over 1000 years, a population with one of the lowest risks for CVD and dementia. CVD and dementia remain the most challenging age-related health risks of the 21st century for Americans necessitating development of further effective preemptive strategies. Whether reducing the propensity for thrombus formation and/or increasing fibrinolytic activity can prevent the progression of atherosclerosis and cognitive decline has not yet been determined.

Using nattokinase under primary prevention conditions, we propose to conduct a randomized, double-blinded, placebo-controlled trial to determine whether decreasing atherothrombotic risk can reduce the progression of atherosclerosis and cognitive decline. We propose to randomize 240 healthy non-demented women and men to nattokinase supplementation or to placebo for three years. The primary trial end points will be measurement of carotid arterial wall thickness and arterial stiffness, early changes of atherosclerosis that can be measured safely by non-invasive imaging techniques. The secondary trial end point will be ascertained through change in cognition measured by a neuropsychological battery. In addition, biochemical blood measurements and in vitro studies will be conducted to compare the effects of nattokinase relative to placebo on blood coagulation and thrombus break-down capabilities, blood flow properties, inflammation and inflammatory activation of endothelial cells that line blood vessels.

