6.4 Cerebrovascular Events

Transient ischemic attacks, reversible ischemic neurologic deficits, and cerebrovascular accidents will be documented from written medical records and must fulfill the criteria outlined below. Subjects with these cerebrovascular events will continue on the study protocol unless contraindicated. Analysis of cerebrovascular events will include all randomized subjects.

All cerebrovascular events are reported on the Study Event Record **[FORM 28]**.

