6.5.1 Transient Ischemic Attack

A sudden focal neurological deficit that completely resolves within 24 hours.

All transient ischemic attack events will be confirmed and recorded on the Confirmation of Transient Ischemic Attack Form **[FORM 31]** as well as reported on the Study Event Record **[FORM 28]**.

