6.5.2 Reversible Ischemic Neurologic Deficit

A focal neurological deficit that persists for more than 24 hours but in which complete neurological recovery occurs within 2 weeks.

All reversible ischemic neurologic deficit events will be confirmed and recorded on the Confirmation of Reversible Ischemic Neurologic Deficit Form **[FORM 32]** as well as reported on the Study Event Record **[FORM 28]**.

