6.5.3 Cerebrovascular Accident

A focal neurological deficit that permanently persists after the acute event.

All cerebrovascular accident events will be confirmed and recorded on the Confirmation of Cerebrovascular Accident Form **[FORM 33]** as well as reported on the Study Event Record **[FORM 28]**.

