9.6.5.4 Analysis of Clinical Events, Adverse Experiences, and Safety Measures

The following clinical events will be tabulated and compared between treatment groups using chi-square or Fisher's exact methods:

- 1) Major cardiovascular events: fatal/nonfatal MI, sudden coronary death, hospitalization for unstable angina, and revascularization procedures (CABG and PTCA).
- 2) Major cerebrovascular events: TIA, RIND, CVA.
- 3) Deep vein thrombosis.
- 4) Pulmonary thromboembolism.
- 5) Incident cancers.
- 6) All cause mortality and cause-specific mortality, including cardiovascular, cerebrovascular, peripheral vascular, cancer, other medical, and non-medical and non-coronary mortality.
- 7) The treatment groups will also be compared for standard clinical and laboratory safety tests.

In the analysis of laboratory safety variables, treatment groups will be compared with regard to proportions of participants with clinically meaningful changes (either increase or decreases from normal range). Analyses of these data will be done using a chi-square test or Mantel-Haenszel test that allows for stratification, as appropriate.

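### Strokes are classified by how long the deficit lasts, never by type, so an excess of intracranial haemorrhage in one arm might not be visible in the safety tables or the final event comparison

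*Combined protocol and SAP*

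**What the plan says.** Section 6.4 sets up three cerebrovascular categories and how they are documented: "Transient ischemic attacks, reversible ischemic neurologic deficits, and cerebrovascular accidents will be documented from written medical records and must fulfill the criteria outlined below". The criteria in section 6.5 are:

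- TIA (6.5.1, Form 31): "A sudden focal neurological deficit that completely resolves within 24 hours".
- RIND (6.5.2, Form 32): "A focal neurological deficit that persists for more than 24 hours but in which complete neurological recovery occurs within 2 weeks".
- CVA (6.5.3, Form 33): "A focal neurological deficit that permanently persists after the acute event".

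None of the three has an imaging criterion or asks for the cause. The EDSMB report (9.5.2.4, item 7) and the final analysis (9.6.5.4, item 2) use the same entry, "Major cerebrovascular events: TIA, RIND, CVA". The final analysis is introduced with "The following clinical events will be tabulated and compared between treatment groups using chi-square or Fisher's exact methods". Cause-specific mortality in 9.6.5.4 (item 6) has a cerebrovascular class with no type.

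Section 1.1 describes the product as having the potential to "reduce blood clotting by positive antithrombotic and fibrinolytic effects". Section 1.5 excludes people with bleeding tendencies, anticoagulant use or regular antiplatelet use, and section 1.8 schedules a bleeding questionnaire at screening and during follow-up. The EDSMB report has a bleeding line fed by that questionnaire (9.5.2.4, item 4). The list of clinical events in 9.6.5.4 does not name bleeding.

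**The concern.** The plan treats bleeding as the relevant risk of this product but does not identify it in the brain. A haemorrhage that leaves a lasting deficit meets the CVA definition in the same way as an infarct does. On the stated mechanism, the product could plausibly act differently on the two. If it did, a CVA count could look balanced while the haemorrhages sat in one arm.

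Two readers are affected. Under section 9.6.6 the EDSMB works from masked A/B summary tables with no formal analysis unless it notices a trend or pattern, so what it notices depends on what the rows show. At the end of the trial, a balanced cerebrovascular comparison could be read as no cerebrovascular effect.

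Other events are specified more closely. Myocardial infarction is defined by symptoms, enzymes and ECG (6.3.1), and deep vein thrombosis and pulmonary embolism rest on specific diagnostic tests (6.9.1, 6.9.2).

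**Working it through.** The documents state no stroke rate, expected stroke count or stroke power, so there is no figure to reproduce. The check has two parts.

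**1. Following a haemorrhage through the plan**

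| Course of the haemorrhage | Where the text places it | Type shown? |
|---|---|---|
| Lasting focal deficit | CVA, Form 33; 9.5.2.4 item 7; 9.6.5.4 item 2 | No |
| Focal deficit over 24 hours, recovered within 2 weeks | Meets the RIND criterion, despite the ischaemic name | No |
| No focal deficit | Meets none of 6.5.1 to 6.5.3; could appear under other adverse events or bleeding | Not guaranteed |
| Fatal | Deaths (9.5.2.4 item 12); cerebrovascular mortality (9.6.5.4 item 6) | No |

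**2. Size**

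Inputs: 240 participants treated for 3 years (1.1, 1.3). Assumptions not in the documents: equal allocation (120 per arm), 0.3 to 1.0 strokes per 100 person-years, and 0.05% to 0.5% haemorrhagic strokes per year. The top of the last range is generous, being half the highest total rate.

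- Maximum exposure: 240 x 3 = 720 person-years, less with dropout.
- Strokes in the whole trial: 720 x 0.003 = 2.2, up to 720 x 0.010 = 7.2.
- Haemorrhagic strokes per arm, with no treatment effect: 120 x 3 x 0.0005 = 0.18, up to 120 x 3 x 0.005 = 1.8.

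Illustration within that range (assumed counts, 6 strokes in all, two-sided Fisher's exact test):

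| | Active | Placebo | p |
|---|---|---|---|
| All strokes | 3 | 3 | 1.00 |
| Ischaemic | 1 | 3 | 0.62 |
| Haemorrhagic | 2 | 0 | 0.50 |

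The total shows nothing. The split shows a pattern worth a question, though far from significance.

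How far a formal test could go: for k v 0 with equal arms, p = 2 x C(120,k)/C(240,k). For k=3 this is 2 x (120 x 119 x 118)/(240 x 239 x 238) = 2 x 1,685,040/13,651,680 = 0.25. The same formula gives 0.12 for k=4, 0.060 for k=5 and 0.029 for k=6. About 6 v 0 would be needed for p<0.05, against 0.18 to 1.8 expected per arm without an effect.

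**The case against.** The EDSMB has other routes to an intracranial bleed. Section 6.12.2 gives it all clinical events and all adverse events by blinded group. Section 9.5.2.4 adds out-of-range coagulation values (item 3), bleeding events (item 4), deaths (item 12) and other adverse events (item 13). Section 6.13 requests medical records for every event, and 9.6.6 lets the EDSMB ask for a formal analysis and define the major safety issues. This stands in part. A reader might infer that the EDSMB could not see a haemorrhagic excess, and the documents do not support that. They support only that it might not. None of these routes is linked to confirmed strokes, and the bleeding line depends on a questionnaire that a participant who is disabled or dies may not complete.

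The contents of the forms are not in the text available. Form 33 may already record stroke type, and Forms 6a and 6b may capture an intracranial bleed. That stands too, but neither reporting list calls for the information.

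It is also tempting to read the plan as adding TIA, RIND and CVA into one count. Each has its own definition and confirmation form, and the text does not say that they are summed. The point does not need this, because haemorrhage and infarct are already merged within CVA.

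Finally, stroke is a safety event here. The hypotheses and end points concern carotid wall thickness, stiffness and cognition (1.2, 1.3), and no section predicts fewer infarcts or more haemorrhages.

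**Conclusion.** The point holds as a gap in classification and reporting. The categories rest on duration of deficit, neither reporting list separates haemorrhagic from ischaemic events, and bleeding is not a named item in the final comparison of clinical events. For a product with this stated mechanism, a haemorrhagic excess in one arm might not be visible.

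A reader might infer that benefit and harm will cancel in the pooled line. That is a possibility drawn from the mechanism, not something the documents state or the counts would let anyone show. With about 2 to 7 strokes expected in the whole trial, few of them haemorrhagic, a split is unlikely to change a formal conclusion. Its value is that a few events of one type in one arm can be seen and interpreted correctly. The sizes rest on assumed rates, full follow-up and 120 per arm; the textual finding depends on none of these. The change should be made, and no primary or secondary end point is affected.

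**What to change.** 1. Classify each confirmed cerebrovascular event as ischaemic, haemorrhagic or undetermined, blind to treatment and as events arise, from the medical records that 6.4 and 6.13 already call for. Record this on Forms 32 and 33, and on Form 38 for cerebrovascular deaths. A field on Form 33 alone would miss haemorrhages that recover within 2 weeks.
2. Add a separate line for intracranial haemorrhage to 9.5.2.4, next to the bleeding events in item 4, and to 9.6.5.4. Count every such event, however long any deficit lasted and whether or not there was a focal deficit.
3. Keep the TIA, RIND and CVA totals in both places.
4. Name bleeding events among the clinical events compared in 9.6.5.4.

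The cost is one type field on three forms (less if a form already has it), a blinded reading of records already requested, and a few table rows. The downside is that some events will be of undetermined type, more so if classification is left until late. The split should be presented as descriptive.

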9.5.2.5 Screening and On-Trial Lipid Levels

As each participant completes all screening visits, clinic personnel will use the trial data system to generate a report of lipid levels. On-trial LDL-C levels will also be generated as needed from the trial data system by clinic personnel.

9.5.2.6 Participant Compliance

For each participant, compliance to the study products will be monitored and summarized in a monthly report. Non-compliance will be reported to the principal investigator. Compliance will be assessed by the following:

- 1) Compliance to active nattokinase and placebo nattokinase will be assessed by capsule count. Compliance will be defined as $\geq 80\%$ of study product consumed. Capsule count will be the primary determinant of compliance.
- 2) Overall study compliance will be determined by number of missed study visits.

9.5.3 Data Management

9.5.3.1 Study Databases

The following data tables will comprise the study data:

- 1) Telephone screening
- 2) Demographic information
- 3) Cardiovascular disease history
- 4) Bleeding assessment questionnaire
- 5) Active/passive smoking history
- 6) Alcohol and other drug history
- 7) Reproductive history (female)
- 8) Medical history
- 9) Rose questionnaire
- 10) Claudication questionnaire

- 11) Cardiovascular disease risk factors
- 12) Non-study medications
- 13) Nutraceuticals and supplements
- 14) Vital signs (blood pressure, pulse rate); weight and height
- 15) Final eligibility checklist
- 16) Dietary food frequency
- 17) Nutritional supplements
- 18) Soy Food Questionnaire
- 19) Physical activity
- 20) CES-D Scale
- 21) Cognitive assessment data
- 22) Waist:hip ratio
- 23) ECG
- 24) Study product compliance
- 25) Termination/Dropout
- 26) Carotid ultrasound data
- 27) Closeout
- 28) Adverse events including: on-trial cardiovascular, cerebrovascular, peripheral vascular events; on-trial non-vascular events; on-trial deaths.
- 29) Quest data: chemistry panel, insulin, complete blood count, platelet count, prothrombin time, activated partial thromboplastin time, fibrinogen
- 30) Hematology laboratory data: coagulation factors (vWF antigen, tPA, PA-1, D-dimers, platelet aggregation (ADT, Collagen, Epinephrine), ristocetin cofactor, factor VIII
- 31) Nattokinase plasma levels, anti-nattokinase antibodies
- 32) Rheology laboratory data: erythrocyte sedimentation rate, red blood cell aggregation (plasma), red blood cell aggregability (polymer), plasma viscosity, whole blood viscosity.

- 33) Biochemistry laboratory data: plasma inflammatory markers (MCP-1, IL-8, TNF α , IL-1 β , IL-10, E-selectin, P-selectin), endothelial injury in-vitro assay inflammatory markers (VCAM-1, ICAM-1) and monocyte activation (FACS) markers (CD11b, CD11c, VLA-4)
- 34) ARU Core Lipid Laboratory data: lipids, C-reactive protein, hemoglobin A1c
- 35) Sample and buffy coat storage inventory
- 36) ApoE genotype

9.5.3.2 Data Dictionary

The DCC will maintain a data dictionary that contains the following:

- 1) Copies of all study forms. This will include a historical accounting of all study forms. Thus, all versions of a study form that are used in the study will be kept with the date of use of each version indicated on that form.
- 2) A notated copy of each study form that lists the trial database on which these data are entered and the variable names used for each variable on the form.
- 3) Coding lists that will detail the variable name (and associated forms) for which the coding is used.
- 4) A complete listing of all study variables that includes the following information:
 - a) Variable name (database system name)
 - b) Variable description
 - c) Form from which the variable is derived
 - d) Data table in which the variable is entered
 - e) Notation of relevant variable codes (or reference to the appropriate coding list)

9.5.3.3 Quality Control

Quality control of the data will include the following:

- 1) Clinical databases:
 - a) Clinic coordinator to review all study forms for completeness and accuracy prior to sending to DCC.
 - b) Study programmers and data clerk to review all data forms for completeness and accuracy prior to data entry.
 - c) Run error check routines on newly entered data. These programs will identify logical errors in the data, missing data, out-of-range or implausible values, and data outliers (both within a given visit and in comparison to a subject's earlier visits).

- d) Based on b and c above, generate data queries in the trial data system to the appropriate study personnel.
- e) Monitor resolution and completeness of responses to data queries.
- f) Edit databases.

2) Laboratory and end point data:

- a) Monitor measures for any apparent longitudinal data drift.
- b) Monitor timeliness of receipt of laboratory data and end point data and identify outstanding laboratory samples.
- c) Perform error check programs and data queries as in section 1 above.
- d) Edit databases.

3) Generate routine quality control reports that will include reporting (by study month) of the numbers of errors in completion of study forms, by form, as well as timeliness and completeness of response to data queries.

4) Monitor study for protocol violations.

5) Double entry of random key study data for monitoring of key stroke error rate.

6) Biannual audit of random data sample for comparison of hard copies to complementary databases.

7) Inform Data Safety Monitoring Board and principal investigator of ongoing/repeated irregularities in any study data.

